**Mapping and Pretreatment evaluation:**

Photographs of the treatment areas will be taken so as not to reveal the subject's identity and identifying information will be coded.

**Wrinkle Classification:**

Each subject will be classified into mild, moderate and severe according to the severity of pre-treatment melasma.

**Photographs:**

Photographs will be taken at each visit prior to treatment and at follow-up visit 4, to evaluate healing time, clinical improvement of melasma, as well as any side effects. Photographs will be taken using the VISIA® Skin Analysis System for facial imaging (Canfield Scientific Inc). This device ensures face position, lighting, photographer, and camera settings are standardized.

Subjects will be asked to remove all skincare products applied to the facial area prior to treatment with a gentle cleanser and clean towel. Participants will be instructed to sit down & place their face in the holder of the VISIA®. This camera will take 3 pictures of the face, including the left, right, and front facial areas. Study staff may need to adjust the height of the chair and or face holding piece inside the VISIA® for subject comfort.

**Laser Parameters:**

Following 15 minutes of topical 30% lidocaine application, patient's side of face that will be treated with Clear & Brilliant 1927nm at treatment level high, with total of 4 passes.

The investigator, the subject, and anyone else in the laser treatment room will wear the appropriate protective eyewear.

**Post-Exposure Skin Care:**

Subjects will be given verbal and written post treatment instructions to clean test sites with warm water and mild soap (Dove™ -- All subjects will be instructed to avoid sun exposure by applying a total block screen with an SPF of 30 or higher and to avoid light exposure to the face for 48 hours after treatment.

**Study Oversight:**

The study will be made available for monitoring, auditing, IRB review and regulatory inspection by providing direct access to study related source data by Ste IRB. The study may be prematurely terminated if the safety of subjects is compromised. Safety evaluations will be determined by the Principal Investigator who may choose to prematurely terminate the study.

Treatment may be discontinued at any time if deemed inappropriate by a physician evaluation. All AEs and SAEs will be monitored by a physician

**Data Management:**

All study data will be stored on a password protected hard drive.

**Intended Use of the Data:**

The expected end use of the data collected will be for the purpose of best practices in treating melasma on the face. As the purpose of the study is to evaluate the safety and efficacy of low energy diode 1927nm, follow-up photos will be examined for melasma improvement by both the investigator(s) and blinded dermatologist reviewers. A satisfaction questionnaire will be given to patients one month after the final laser treatment. Photos and the satisfaction questionnaire will be examined by the principal investigator and sponsor to determine best practices for use of low energy diode 1927nm in treating melasma in face.

**Clinical Evaluations:**

The following clinical evaluations will be performed throughout the study as detailed in the visit procedure summary. In the event a treatment is to be administered at a visit the scoring should be done before any laser therapy or drug application. The same investigator should complete the evaluations for a given subject throughout the study. If this becomes impossible a sub investigator with overlapping experience with the subject and the study should complete the evaluations.

**Wrinkle evaluation:**

Evaluation of fine wrinkling only in the facial area.

- 0- None
- 1- Minimal
- 2- Mild
- 3- Moderate
- 4- Severe

**Tactile Roughness:**

Texture of the overall face skin assessed by lightly palpating by stroking gently with the index finger.

- Skin is very smooth
- Skin is smooth with very occasional roughness
- Mild roughness
- Moderate roughness
- Severe roughness

**Mottled Hyperpigmentation**

- Evenly Pigmented Skin
- Light Hyperpigmentation involving small areas
- Moderate hyperpigmentation involving moderate sized areas; Light hyperpigmentation involving moderate areas
- Moderate hyperpigmentation involving moderate sized areas; light hyperpigmentation involving large areas; small areas of heavy pigmentation
- Heavy hyperpigmentation

All subjects who drop out before the final examination will be maintained in the study for accountability reasons. Any adverse effects that occur, irrespective of subject compliance with the complete follow-up examination schedule, will be reported in the study results.

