The primary objective of our study is to determine the efficacy of combined topical cysteamine cream with a 1927 diode non-ablative laser (Clear + Brilliant Permea®; Solta Medical, Inc.), compared to topical cysteamine alone in the treatment of melasma. This efficacy will be assessed using modified Melasma Area and Severity Index (mMASI) scores, a validated physician assessment tool, at baseline and at follow up visits at week 4, 8 and 12 as well as Investigator Global Assessments. Secondary objectives also include an assessment of patient satisfaction which will be evaluated via patient questionnaires distributed to patients at baseline and at week 12. In addition, impact on quality of life will also be assessed utilizing the melasma quality of life scale (MELASQoL) questionnaire which will be administered to patients at baseline and at week 12.

Multiple studies have demonstrated the efficacy of topical cysteamine in the treatment of melasma. Mansouri et al. conducted a double-blind, randomized, controlled clinical study, which included 50 melasma patients, and demonstrated significant efficacy of topical cysteamine in the treatment of melasma. One comparative trial demonstrated that topical 5% cysteamine, though safe and well-tolerated, was less effective than topical 4% hydroquinone in the treatment of facial melasma; however, a later published response indicated that the concentration of cysteamine may have been less than the reported 5%. A single-blind, randomized comparative trial of 54 melasma patients found no statistically significant difference in the efficacy of topical cysteamine compared to topical tranexamic acid; however, cysteamine was better tolerated amongst the patients. Finally, Karrabi et al. also found that cysteamine 5% cream showed greater efficacy than the gold standard, modified Kligman's formula, in their randomized, double-blind trial of 50 patients with epidermal melasma.

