**Criteria of Evaluation (Study Endpoints):**

In person assessment by treating physician and photographic assessment in which blinded dermatologists compared photographs of the individual's face areas at baseline and visit 4 from all patients in the study.

Clinical Endpoints:

- In person assessment by treating physicians will measure change in mMASI of the subjects face at between baseline (visit 1) and week 4.
- The Global Aesthetic Improvement Scale (GAIS), a 5-point scale rating global aesthetic improvement in appearance, compared to pretreatment, as judged by the investigator and the subject will also be assessed. The rating categories used on this scale will be “worse” “no change” “improved” “much improved” and “very much improved”. The percent ranking improvements in the Investigator and Subject GAIS scale from baseline (visit 1) to visit 4 will be compared.
- Photographic assessment by two blinded dermatologists will measure changes will assess improvement in melasma by mMASI score. In addition, an investigator quartile improvement score from baseline to week 12 (0 – 0%, no improvement; 76%-100% - very significant improvement) will be assessed.

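### Three clinical evaluations are required that no endpoint or visit list uses, the mottled-pigment scale among them has overlapping and missing grades, and the melasma-grading step names no instrument

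*Protocol*

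**What the plan says.** The protocol's Clinical Evaluations section opens with an instruction: "The following clinical evaluations will be performed throughout the study as detailed in the visit procedure summary". It adds two conduct rules: score before any laser or drug application, and keep the same investigator for a given subject. Three scales follow directly:

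- Wrinkle evaluation: "Evaluation of fine wrinkling only in the facial area"
- Tactile Roughness: "Texture of the overall face skin assessed by lightly palpating by stroking gently with the index finger"
- Mottled Hyperpigmentation: five grades. The third reads "Moderate hyperpigmentation involving moderate sized areas; Light hyperpigmentation involving moderate areas" and the fourth "Moderate hyperpigmentation involving moderate sized areas; light hyperpigmentation involving large areas; small areas of heavy pigmentation".

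The efficacy instrument is set out elsewhere. The Background section says of the primary objective: "This efficacy will be assessed using modified Melasma Area and Severity Index (mMASI) scores, a validated physician assessment tool", at baseline and weeks 4, 8 and 12. Criteria of Evaluation (Study Endpoints) gives it to the treating physician, "In person assessment by treating physicians will measure change in mMASI of the subjects face at between baseline (visit 1) and week 4", and to the photograph readers, "Photographic assessment by two blinded dermatologists will measure changes will assess improvement in melasma by mMASI score". A table after that defines area, darkness, regional weights and a total of 0 to 24.

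The visit lists under Procedure include a melasma-grading step at Visits 1 and 4 only and do not say which instrument it uses. They contain no wrinkle or roughness scoring.

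**The concern.** The instruction to perform the three scales refers to visit procedures that do not contain them, and the grading step that the visits do contain is not tied to a scale. Three candidates could be meant: the mild/moderate/severe melasma classification (printed under the heading Wrinkle Classification), the mottled-pigment scale, and mMASI. The mottled-pigment scale is the pigment measure printed directly under the instruction to perform evaluations.

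If it is scored, some faces can be given either of two grades and others fit none, so a recorded change between visits need not reflect a change in the skin. The trial also compares two sides of one face, one randomly selected for laser. Roughness is rated for the face overall, and neither the wrinkle nor the pigment scale has a per-side instruction. As written, none of the three can inform the laser comparison.

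**Working it through.** **1. Are the three scales used anywhere?**

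| Item | Wrinkling | Roughness | Mottled pigment | mMASI |
|---|---|---|---|---|
| Listed directly after the Clinical Evaluations instruction | yes | yes | yes | no |
| Named in the Study Endpoints text | no | no | no | yes |
| Named in the visit lists | no | no | no | no (an unnamed melasma grading at Visits 1 and 4) |

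**2. Can the mottled-pigment scale be scored?** Grades are counted by their order in the list. Each combination of intensity (light, moderate, heavy) and area (small, moderate, large) is placed in every grade whose wording covers it. The fifth grade, heavy pigmentation, states no area limit and is read literally.

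| | Small areas | Moderate areas | Large areas |
|---|---|---|---|
| Light | 2nd | 3rd | 4th |
| Moderate | none | 3rd and 4th | none |
| Heavy | 4th and 5th | 5th | 5th |

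- Exactly one grade: light/small, light/moderate, light/large, heavy/moderate, heavy/large = 5.
- Two grades: moderate/moderate, heavy/small = 2.
- No grade: moderate/small, moderate/large = 2.
- Without a unique grade: 2 + 2 = 4 of 9.

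If the fifth grade is taken to exclude small areas, heavy/small becomes unique and the count is 3 of 9. On either reading no moderate-intensity combination has a unique grade.

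**3. Is mMASI complete as defined?** Maximum = (0.3 + 0.3 + 0.3 + 0.1) × 6 × 4 = 24, which agrees with the stated range. It can be scored for the whole face. For a side-by-side comparison, the two malar regions already belong to one side each, but forehead and chin do not. They carry 0.3 + 0.1 = 0.4 of a total weight of 1.0. The whole-face total therefore cannot separate the laser side from the cysteamine-only side.

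**4. What would a per-side score look like?** Dividing forehead and chin at the midline halves their weights: 0.3/2 = 0.15 and 0.1/2 = 0.05. Half-face maximum = (0.15 + 0.3 + 0.05) × 6 × 4 = 0.5 × 24 = 12, and the two sides' maxima add to 24.

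**5. When is mMASI scored?** The Background section says baseline and weeks 4, 8 and 12. The in-person endpoint says baseline to week 4. The visit lists place melasma grading at Visits 1 and 4 (week 12). These three do not agree.

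**The case against.** A reader might infer that the protocol prescribes these scales in place of mMASI, or that the mottled-pigment scale is its only pigment measure. The documents do not support that. mMASI is the named efficacy measure, the endpoint text assigns it to both the treating physician and the blinded readers, and its table is complete. The table of contents runs from Clinical Evaluations (continued) on page 11 straight to Risks on page 12, with no separate endpoints entry, so the mMASI text probably belongs to the same section. The treating physician's mMASI is also the natural meaning of the grading step. Because the visit lists schedule no wrinkle or roughness scoring, those scales may simply never be scored.

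It is also tempting to say that the pigment scale cannot be scored reproducibly at all, or that a typical patient could shift by a fixed fraction of it. Five of the nine combinations have a single grade, the protocol gives no distribution of severity, and its ordered categories are not stated to be equally spaced. Mottled pigment could also plausibly serve the objective of clinician-judged improvement.

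All of this stands, and it limits the point. What remains is an instruction that does not match the visit lists, a grading step without a named instrument, and a duplicated descriptor. Keeping the same investigator limits differences between raters, but one rater can still choose either of two overlapping grades. The Wrinkle Classification heading and the mention of neck and chest rhytides under Risk Management suggest text carried over from another protocol, but that is an inference and nothing here depends on it.

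**Conclusion.** The point holds in limited form and should be corrected. The protocol requires three evaluations that no endpoint names and no visit list schedules. One of them gives no unique grade for 4 of 9 intensity-by-area combinations (3 of 9 on the lenient reading). The count assumes three intensity and three area levels, taken from the scale's own wording. It says nothing about how many subjects would be affected.

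Because no endpoint uses the mottled-pigment scale, its fault does not itself bias the mMASI comparison. The consequences are data that cannot be interpreted if the scale is scored, and uncertainty about which instrument the grading step means. A related gap is that the rules on scoring before treatment and on keeping the same investigator are attached to the evaluations that follow them. Whether they cover mMASI depends on where that section ends.

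**What to change.** 1. Delete the Wrinkle evaluation, Tactile Roughness and Mottled Hyperpigmentation scales. If the pigment scale is kept as a supportive measure, make its grades mutually exclusive and complete: give moderate/moderate one grade, place moderate/small and moderate/large, and bound the top grade. Score it per side.
2. State under Procedure that melasma grading means the mMASI of the protocol's table, scored separately for each side with forehead and chin divided at the midline. Half-face weights of 0.15 (forehead), 0.3 (malar) and 0.05 (chin), maximum 12 per side, are one example.
3. State that the Clinical Evaluations rules on scoring before treatment and on the same investigator apply to mMASI.
4. Reconcile the visits at which mMASI is scored across the visit lists, the Background section and the Study Endpoints text.

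The cost is a change to protocol wording and the case report form, with slightly more scoring detail because two regions are divided. The protocol calls mMASI validated but defines only a whole-face score, so the half-face version should be described as an adaptation. Deleting the three scales removes assessments, and naming the instrument adds no visits.

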**Criteria of Evaluation (Study Endpoints):**

In person assessment by treating physician and photographic assessment in which blinded dermatologists compared photographs of the individual's face areas at baseline and visit 4 from all patients in the study.

Clinical Endpoints:

- In person assessment by treating physicians will measure change in mMASI of the subjects face at between baseline (visit 1) and week 4.
- The Global Aesthetic Improvement Scale (GAIS), a 5-point scale rating global aesthetic improvement in appearance, compared to pretreatment, as judged by the investigator and the subject will also be assessed. The rating categories used on this scale will be “worse” “no change” “improved” “much improved” and “very much improved”. The percent ranking improvements in the Investigator and Subject GAIS scale from baseline (visit 1) to visit 4 will be compared.
- Photographic assessment by two blinded dermatologists will measure changes will assess improvement in melasma by mMASI score. In addition, an investigator quartile improvement score from baseline to week 12 (0 – 0%, no improvement; 76%-100% - very significant improvement) will be assessed.

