### Procedure:

#### Visit 1 (Screening and Initial Treatment Visit)

- Verify that subject is qualified to participate in the study.
- Ask subject to give personal information, such as name, date of birth, race and ethnicity.
- Review medical and dermatology (skin) history, including history of previous treatments to area being treated.
- Review past and current medications and skin care products.
- See how tall subject is and how much subject weighs
- If subject is a woman and can have children, urine will be tested to see if subject is pregnant. The study doctor or study staff will tell subject if pregnancy test results are positive. The results of the pregnancy testing must be negative in order for subject to be in the study.
- Supply patient with topical cysteamine cream and review instructions for its use
- Identify and examine the area (i.e, side) of face to which the Diode 1927 nm laser will be used (mapping)
- Take photos of face
- Perform grading of melasma
- Perform treatment according to guidelines stated in protocol
- Schedule the next study visit

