**Objectives:**

- A. To evaluate the efficacy of the Clear & Brilliant Permea laser system in combination with topical cysteamine
  - a. To assess for improvement of melasma after completion of three treatments as determined by the treating clinician and objective measures
  - b. To evaluate subject's satisfaction with melasma treatment and assessment of improvement after three treatments
  - c. To evaluate the length of treatment.
- B. To evaluate the safety of melasma treatment in all skin types using the Clear & Brilliant Permea laser in combination with topical cysteamine
  - a. To evaluate the immediate response to treatment
  - b. To evaluate the subject's assessment of comfort associated with treatments
  - c. To determine the rate of adverse events for the treatment group as a whole

**Study Design:** Single Center, Prospective, With Before-After Analysis

**Study population:** Twenty healthy male or female patients, 18-74 years of age, of all skin types with melasma on the face that wish to be treated. Each subject will receive topical cysteamine cream which they will be instructed to use once a day at home. In addition, one side of the face will be randomly selected for treatment with laser. Patients will receive three monthly treatments, at 4-6 week intervals, on the selected side of the face with the Clear & Brilliant Permea laser. The treatment duration including pre and post treatment procedures is estimated to be 90 minutes per subject. Subjects will return for a follow-up visit 3 months after the initial treatment for a total of four visits. The treatment plan will be the same regardless of the subject's skin type. Four passes, at high setting will be performed.

During the first and fourth visit, the areas of treatment will be photographed with a digital camera under controlled conditions. Subject improvement will be assessed via investigator and subject grading at visit 1 and 4. Improvement in melasma will be assessed by blinded evaluators who will review pre and post treatment photographs taken with VISIA® Skin Analysis System for facial imaging (Canfield Scientific Inc) from visit 1 and 4. Side effects (including pain, redness, dryness, and hyperpigmentation) will be assessed and recorded at visits 2, 3, 4.

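### Two mMASI ratings serve the primary objective and neither is ranked; the blinded photographic rating, scored by side, should be named primary

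*Protocol*

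**What the plan says.** The objective paragraph in the Protocol's Background section sets the primary objective as combined treatment versus cysteamine alone. "This efficacy will be assessed using modified Melasma Area and Severity Index (mMASI) scores, a validated physician assessment tool", it says, at baseline and weeks 4, 8 and 12, "as well as Investigator Global Assessments". It names no rater.

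The section Criteria of Evaluation (Study Endpoints) then gives two mMASI ratings as parallel clinical endpoints:

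- Open: "In person assessment by treating physicians will measure change in mMASI of the subjects face at between baseline (visit 1) and week 4".
- Blinded: "Photographic assessment by two blinded dermatologists will measure changes will assess improvement in melasma by mMASI score".

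GAIS (investigator and subject) and a quartile improvement score are listed with them. No endpoint is called primary. Objective A.a judges improvement "as determined by the treating clinician and objective measures", and Intended Use of the Data has the photographs examined by investigators as well as blinded reviewers.

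On design, the study population paragraph under Objectives says "one side of the face will be randomly selected for treatment with laser". Neither that paragraph nor Laser Parameters describes a sham on the other side. Visit 1 includes the step "Identify and examine the area (i.e, side) of face to which the Diode 1927 nm laser will be used (mapping"), listed ahead of photographs and grading. Clinical Evaluations asks that the same investigator rate a given patient throughout, and that scoring precede any laser or drug application at a visit.

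**The concern.** Each patient is their own control, so the primary question is answered by a difference between two sides of one face. A rater who knows which side was lasered, and expects it to do better, can shift that difference directly. Randomising the side does not protect against this, and a larger sample does not remove it: a fixed bias becomes more likely to reach significance as the sample grows.

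The protocol plans a rating on the same scale that could largely avoid the problem, but nothing makes that rating carry the conclusion. Which rating is primary, who is masked to what, and how a side is scored all determine how the data are collected. A later analysis plan cannot restore masking that was absent when the scores were made.

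**Working it through.** **1. What the protocol states about each rating**

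| Feature | In-person mMASI | Photographic mMASI |
|---|---|---|
| Rater | Treating physicians | Two dermatologists |
| Blinding | None stated | Called blinded; to what is not said |
| Time points | Baseline to week 4 (endpoint section); grading at visits 1 and 4 (visit lists) | Visits 1 and 4 |
| Rank | None | None |

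**2. The plan's own sample size.** Sample Size Calculation gives 20 patients, 80% power and a paired t-test, called one-sided in one sentence and two-sided at 5% in the next. It gives no effect size or SD, so the 20 cannot be reproduced. Solved backwards with the noncentral t, 20 patients detect a standardised paired difference of 0.66 (two-sided) or 0.58 (one-sided). This gives a scale for the bias sizes in step 3.

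**3. Effect of a rating bias.** Inputs: no true side difference; n = 20 (Protocol); two-sided alpha 5% (Protocol); bias b in SD units of the paired difference (assumed, since the protocol gives none).

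Noncentrality = b × √n, with df = n − 1 = 19 and critical value 2.093.

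| b (assumed) | b × √20 | Rejects in favour of laser | Rejects in either direction |
|---|---|---|---|
| 0 | 0 | 2.5% | 5.0% |
| 0.1 | 0.447 | 6.2% | 7.1% |
| 0.2 | 0.894 | 13.3% | 13.6% |
| 0.3 | 1.342 | 24.6% | 24.7% |

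Two variants follow from the protocol's own wording. A one-sided 5% test at n = 20 rejects about 11%, 22% and 36% of the time. With all 25 permitted patients evaluable, the two-sided test rejects about 8%, 16% and 30%.

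**4. Can the planned mMASI separate the sides?** The mMASI table weights area (0 to 6) times darkness (0 to 4):

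- each malar region: 0.3 × 6 × 4 = 7.2, scored separately for left and right
- forehead: 0.3 × 6 × 4 = 7.2, undivided
- chin: 0.1 × 6 × 4 = 2.4, undivided

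Forehead plus chin is 7.2 + 2.4 = 9.6 of 24 points, or 40%. The whole-face total therefore cannot serve as a laser versus non-laser measure. The malar score of each side (0 to 7.2) can, without changing the table.

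**5. Time points.** The endpoint section has week 4 for the in-person mMASI. The objective paragraph and hypothesis 1 have weeks 4, 8 and 12. The visit lists schedule grading at visit 1 and visit 4 (week 12) only; the list for visits 2 and 3 has no grading. The study population paragraph also places grading at visits 1 and 4.

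**6. Gap between last laser treatment and visit 4.** The visit list puts treatments 2 and 3 at weeks 4 and 8, so the gap is 12 − 8 = 4 weeks. That fits the questionnaire one month after the last treatment in Intended Use of the Data. The study population paragraph says "Patients will receive three monthly treatments, at 4-6 week intervals". Two intervals of 4 to 6 weeks put the third treatment at weeks 8 to 12, so the gap would be 4 to 0 weeks if visit 4 stays at week 12. Zero is the worst case, reached only if both intervals run to six weeks. The gap matters here because a reaction such as erythema or edema, listed under Subject Risks, could show readers the treated side.

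**The case against.** **The blinded reading is already there.** It is, which is why the change is cheap. It is not ready to use, though: the protocol does not say what readers are blinded to, defines no side score, and gives the reading no priority.

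**This can be left to the analysis plan.** Combining two readers' scores and the mechanics of masking may well be settled there or in a reading guide, and they are not raised here. The protocol itself, however, gives two ratings equal standing under one primary objective, and it fixes how raters work.

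**Scoring precedes treatment at each visit.** True, and this partly answers the order of steps at visit 1, where list order may not be strict sequence. It does not keep the side from a rater who has mapped it, or from the same investigator at visit 4.

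**The side contrast is not settled as the primary question.** The study design line describes a before-after analysis, and the null hypothesis names no comparator. The objective and hypotheses, however, clearly compare combined treatment with cysteamine alone. The mismatch stands and belongs in the fix.

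**Stronger readings a reader might infer.** The protocol does not say that the treating physicians are unblinded; that is an inference, though a sound one. Nor does it choose the open score as primary: it chooses neither. And it does not plan photographs immediately after a treatment, since the visit list leaves four weeks.

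**Conclusion.** The concern holds in this form: two mMASI ratings stand unranked under one primary objective, blinding is stated only for the photographic readers, and a conclusion drawn from the open rating would be exposed to bias in the very contrast the trial is meant to estimate.

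The percentages illustrate how sensitive a paired test would be. They do not estimate bias in this trial. They rest on assumed biases of 0.1 to 0.3 SD, no true effect, and an analysis by paired t-test; the protocol allows that a different model may be used.

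Masked reading would reduce the bias and might not remove it, because visible laser reactions may partly unmask the readers. The point should be corrected before data are collected. It does not invalidate the design, because the means of correcting it are already planned.

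**What to change.** 1. **One primary measure.** In the objective paragraph and the endpoint section, name the blinded photographic mMASI change from visit 1 to visit 4 (week 12), laser side versus non-laser side. State that readers are masked to the lasered side.
2. **Side score.** Use the malar score of each side (0 to 7.2). Report the whole-face total descriptively.
3. **Ranking.** Make the treating physician's mMASI, the Investigator Global Assessments, GAIS, the quartile score and the investigators' photograph review secondary.
4. **Alignment.** Bring objective A.a, the before-after design label and the null hypothesis into line with the side contrast.
5. **Time points.** Reconcile week 4 in the endpoint section, weeks 4, 8 and 12 in the objective and hypothesis 1, and the visit lists, which grade at visits 1 and 4 only.
6. **Baseline order.** Take baseline photographs and grading before the lasered side is identified.
7. **Schedule, as a separate matter.** The treatment intervals in the study population paragraph, the treatment weeks in the visit list, visit 4 at week 12 and the one-month interval in Intended Use of the Data must be reconciled.

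**Cost.** Low. The two readers, the visit 1 and visit 4 photographs, and the left, right and front views are already planned. The additions are text, a masking rule and a side score.

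**Downsides.** Photographs may be less sensitive than live grading (an assumption), which is why live grading stays as secondary. The malar score leaves out forehead and chin.

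### The in-person mMASI endpoint is set at week 4, after one of three laser sessions and at a visit with no grading listed; the rest of the protocol points to visit 4

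*Protocol*

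**What the plan says.** Under Criteria of Evaluation (Study Endpoints), the treating physician's in-person assessment is to measure "change in mMASI of the subjects face at between baseline (visit 1) and week 4". Other parts of the protocol bear on that time point:

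- **Same section.** The GAIS endpoint reads "Investigator and Subject GAIS scale from baseline (visit 1) to visit 4 will be compared". The photographic part adds "an investigator quartile improvement score from baseline to week 12". The opening sentence sets the blinded photograph comparison at baseline and visit 4.
- **Objectives, item A.a.** "To assess for improvement of melasma after completion of three treatments", as judged by the treating clinician and by objective measures.
- **Study population.** "Subject improvement will be assessed via investigator and subject grading at visit 1 and 4". Also "Patients will receive three monthly treatments, at 4-6 week intervals", and "Subjects will return for a follow-up visit 3 months after the initial treatment for a total of four visits".
- **Procedure.** Visits 2 and 3 are weeks 4 and 8; visit 4 is week 12. Grading of melasma is listed at visits 1 and 4. It is absent from the list for visits 2 and 3, which covers side effects, height and weight, treatment, scheduling and photographs.
- **Clinical Evaluations.** At a visit with treatment, "the scoring should be done before any laser therapy or drug application".
- **Background (primary objective) and hypothesis 1.** Both place mMASI at weeks 4, 8 and 12.
- **Intended Use of the Data.** The satisfaction questionnaire is given one month after the last laser session.

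**The concern.** The protocol contains three mMASI schedules that cannot all hold: week 4 alone (the endpoint definition), weeks 4, 8 and 12 (the primary objective and hypothesis 1), and visits 1 and 4 (the visit procedures and Study population).

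mMASI is the first measure named for the primary objective. If the endpoint line is followed as written, the in-person change either has no score behind it, because visit 2 has no grading, or describes the skin after one laser session. Neither answers objective A.a. If the conflict stays open until the data are in, the time point for this measure would be chosen after the results are known. An in-person score missed at a visit cannot be recovered later.

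**Working it through.** There is no planned figure to reproduce. The sample size paragraph gives 20 subjects without an effect size, a standard deviation or a time point, so correcting the endpoint date does not alter the stated number. The check is a count of sessions.

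**Inputs**

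- Three sessions, spaced *k* = 4, 5 or 6 weeks (Study population), given at weeks 0, *k* and 2*k*.
- Scoring comes before treatment at a treatment visit (Clinical Evaluations).
- Visit 2 = week 4, visit 3 = week 8, visit 4 = week 12 (Procedure).
- Assumption: one month is taken as 4 weeks.

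**Formulas**

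- Sessions before a score at week *w* = number of sessions dated strictly before *w*.
- Gap from session 3 to a week-12 score = 12 − 2*k*.
- One month after session 3 = 2*k* + 4.

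| | *k* = 4 | *k* = 5 | *k* = 6 |
|---|---|---|---|
| Session weeks | 0, 4, 8 | 0, 5, 10 | 0, 6, 12 |
| Sessions before a week-4 score | 1 | 1 | 1 |
| Sessions before a week-8 score | 2 | 2 | 2 |
| Sessions before a week-12 score | 3 | 3 | 2 |
| Weeks from session 3 to week 12 | 12 − 8 = 4 | 12 − 10 = 2 | 12 − 12 = 0 |
| Week of session 3 + one month | 8 + 4 = 12 | 10 + 4 = 14 | 12 + 4 = 16 |

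**Reading the table**

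1. A week-4 score reflects 1/3 = 33% of the sessions at every permitted spacing. Calendar week 4 coincides with visit 2 only at 4-week spacing. At 5 or 6 weeks no visit falls in week 4. If the endpoint is then taken to mean visit 2, the score still precedes session 2, so the count remains 1.
2. Week 12 and visit 4 as the post-treatment follow-up agree cleanly only at 4-week spacing. At 6 weeks a week-12 score falls on the day of session 3, before it is given, after 2/3 = 67% of sessions. If three months is read as 52/4 = 13 weeks, the gaps become 5, 3 and 1 weeks, so follow-up still varies by four weeks.
3. The questionnaire one month after the last session meets week 12 only at 4-week spacing; otherwise it falls at week 14 or 16.

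The endpoint sentence pairs a visit number for its start with a week number for its end. Together with the GAIS line directly after it, this makes a slip for visit 4 the likeliest explanation, though the text does not prove it.

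**The case against.** The best case on the other side is that this is a one-word slip which the surrounding text corrects. The opening sentence of the endpoint section can be read as dating both the in-person and the photographic assessment at visit 4, and grading at visit 4 is in the procedures. Post-treatment scores would therefore exist whichever way the line is read, and two blinded dermatologists also score mMASI from photographs. On this view the harm is small and the spacing arithmetic is a separate scheduling matter, since everything agrees at visits in weeks 0, 4, 8 and 12.

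Part of this stands. The photographic comparison is intact, no effect on the error rate or the sample size is shown, and the 6-week case is the extreme of the permitted range. It is also true that week 4 is a planned mMASI time point in the primary objective and hypothesis 1, so it is not foreign to the protocol.

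It does not remove the problem. Those statements list week 4 beside weeks 8 and 12, never alone, and the visit list provides no grading at weeks 4 or 8. Reading the opening sentence as covering both assessments puts the contradiction inside a single section. Collecting a visit-4 score does not correct an endpoint defined at week 4.

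One could also argue that the score-before-laser rule is meant for the wrinkle, roughness and pigmentation scales printed after it. But the rule covers the evaluations set out in the visit procedures, and those include melasma grading.

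**Conclusion.** The concern holds, and the endpoint line must be corrected. As written, the in-person mMASI endpoint falls after 1 of 3 laser sessions, at a visit without scheduled grading, and contradicts objective A.a, the grading schedule and the other endpoints in its own section. The count rests on the stated session intervals and on scoring before treatment. The week 12, 14 and 16 figures also rest on a 4-week month. The finding does not depend on week 4 being a slip: the passages need reconciling under either reading. It is confined to the in-person score. No claim is made about false-positive rate or power.

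**What to change.** 1. In Criteria of Evaluation (Study Endpoints), change week 4 to visit 4 in the in-person mMASI line. State that this is the follow-up visit after all three sessions and that it is the single primary time point for the in-person mMASI.
2. Define visit 4 in one way across Procedure, Study population, Intended Use of the Data and the endpoint section, and reconcile that definition with the permitted treatment intervals. No interval is proposed here.
3. In the primary objective and hypothesis 1, either delete weeks 4 and 8 or label them secondary. If they are kept, add melasma grading to visits 2 and 3, or score the photographs from those visits. In the second case, first reconcile the photograph schedule: Procedure and Photographs provide for pictures at visits 2 and 3, while Study population mentions only the first and fourth visits.

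The cost is wording: one endpoint line, one definition of visit 4, and alignment of the objective, hypothesis and visit list. Keeping weeks 4 and 8 adds a short grading or photograph scoring at two visits per subject.
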